Treatment comparisons for duration of joint stiffness will be analyzed using a nonparametric method using the Hodges-Lehmann estimator. For the comparison between each baricitinib group and placebo group, the median difference of change from baseline score and its 95% CI from the Hodges-Lehmann estimator will be presented. The p-value for the median difference of change from baseline will be calculated using the Wilcoxon rank-sum test. A 95% CI for the median change from baseline score within each treatment group will be calculated using distribution-free confidence limits.

Time to first flare analyses will be analyzed using a Cox proportional hazards model with treatment group, with disease activity (total SLEDAI-2K <10; \geq 10), baseline corticosteroid dose (<10 mg/day; \geq 10 mg/day prednisone or equivalent), and region (North America, Central/South America/Mexico, Europe, Asia and Rest of World) fitted as explanatory variables. Hazard ratios, median time to flare, 95% CI and p-values will be presented for treatment comparisons to placebo. Only if flares occurred during the flare exposure time period (defined below for each datapoint set, respectively) will be counted as an event. For severe SFI flare, only the eligible severe flares will be counted (See 6 criteria for identifying eligible severe SFI flares in [Appendix 5](#)). Patients who do not have an event during the flare exposure time period will be censored at the end of the flare exposure time. The flare exposure time varies with different datapoint sets ([Table JAIA.6.5](#)).

- For the PPCV datapoint set, while considering the treatment effect without potentially confounding influences of COVID-19, the flare exposure time is defined as the time after the date of the first dose of study drug to the prohibited medication start date, treatment discontinuation date, study discontinuation date or date of the Week 52 visit, whichever is earlier, and excluding the time period of treatment interruption due to COVID-19 from the interruption start date plus 20 days to the interruption end date plus 20 days, both inclusive, if the interruption duration is 20 days or more.

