- For the PP datapoint set, which ignores treatment interruption due to COVID-19, the flare exposure time is defined as the time after the date of the first dose of investigational product to the prohibited medication start date, treatment discontinuation date, study discontinuation date or date of the Week 52 visit, whichever earlier.
- For the As Collected (AC) datapoint set, which considers all collected data, the flare exposure time is defined as the time after the date of the first dose of investigational product to the study discontinuation date or date of the Week 52 visit, whichever earlier.

The annualized flare rate will be calculated as the number of flares divided by the flare exposure time in days multiplied with 365.25, where the flare exposure time is defined above and varies with the different datapoint sets. The number of flares includes the flare events that happened during the flare exposure time period. All collected flares, including mild/moderate and severe flares will be considered eligible for the analysis.

For comparing the flare rate in the baricitinib treatment group versus the placebo, the negative binomial regression model will be applied. The response variable in the model will be the number of flares during the flare exposure time with baseline disease activity (total SLEDAI-2K <10; ≥ 10), baseline corticosteroid dose (<10mg/day; ≥ 10 mg/day prednisone or equivalent), region (North America, Central/South America/Mexico, Europe, Asia and Rest of World) as explanatory variables. The natural logarithm of the flare exposure time will be used as an offset variable in the model to adjust for patients having different exposure times. The estimated rate ratio and the corresponding 95% CI, as well as the 2-sided p-value will be presented. When the negative binomial regression does not converge or the parameters cannot be estimated, an exact Poisson regression will be applied to calculate the rate ratio, 95% CI and the p-value.

Fisher's exact test will be used for patient disposition, adverse events (AEs), discontinuations, and other categorical safety data for between-treatment group comparisons. Continuous vital signs, body weight, and other continuous safety variables including laboratory variables will be analyzed by ANCOVA with treatment and baseline value in the model. Shift tables for select categorical safety analyses (for example, "high" or "low" laboratory results) will also be produced.

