Appendix 5. Time to First Severe Flare

In the time to first severe SFI flare analysis, only severe flares in patients who were eligible for that particular flare, as described below, will be counted. For example, a severe flare based on an increase in SLEDAI score to greater than 12 would only be counted in patients with a SLEDAI score of 12 or less at baseline. This would avoid the issue of a patient with a SLEDAI score of greater than 12 at baseline requiring an improvement in SLEDAI score prior to being eligible for flare based on that criterion. Those patients with a baseline SLEDAI score greater than 12 would be eligible for counting as a flare from other criteria, but not from that particular criterion.

There are 6 criteria to identify severe flares that are eligible to be counted in the time to severe flare analysis as showed below:

1. *Increase in SLEDAI score to greater than 12*

Limit patients who can be counted as having a severe flare by this criterion to patients who have SLEDAI score ≤ 12 at baseline.

2. *New or worsening (requiring doubling the prednisone dose or increase in prednisone dose to more than 0.5 mg/kg per day or acute hospitalization) of one or more of the following: Central nervous system involvement, Glomerulonephritis, Hemolytic anemia (hemoglobin less than 70g/L or decrease of 30 g/L), Myositis, Thrombocytopenia (platelets less than 60,000/L), or Vasculitis (more than cutaneous involvement)*

A patient would be counted as having a flare by this criterion if they do not have a baseline flare on the same component at baseline. For example, if a patient's case report form indicates that they had a postbaseline flare due to glomerulonephritis, this flare would only count in the analysis if they didn't have a severe baseline flare based on glomerulonephritis. That is, if that patient had a baseline flare due to central nervous system involvement, but not due to glomerulonephritis, the post-baseline flare due to glomerulonephritis would be counted in the analysis.

3. *Increase in prednisone (or equivalent) to more than 0.5 mg/kg/day*

Limit patients who can be counted as having a severe flare by this criterion to patients who have a prednisone dose of ≤ 0.5 mg/kg/day at baseline.

4. *Initiation of immunosuppressive therapy*

Limit patients who can be counted as having a severe flare by this criterion to patients who were not in flare at baseline based on this criterion.

5. *Hospitalization for lupus activity*

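### Time to first severe flare (PPCV, PP): a severe flare defined by a prohibited drug change is dropped if it is dated after that change, and the patient is censored at the change

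*SAP*

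**What the plan says.** **Window.** SAP Section 6.4 defines flare exposure separately for each datapoint set. For PPCV it is the "time after the date of the first dose of study drug to the prohibited medication start date", or to treatment discontinuation, study discontinuation or the Week 52 visit if earlier, with some COVID-19 interruption time removed. For PP it is the "time after the date of the first dose of investigational product to the prohibited medication start date", with the same alternatives and no COVID-19 exclusion. The AC window does not stop at prohibited medication.

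**Events and censoring.** Only flares inside the window count. "Patients who do not have an event during the flare exposure time period will be censored at the end of the flare exposure time". The annualized rate follows the same window: "The number of flares includes the flare events that happened during the flare exposure time period".

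**Status.** Table JAIA.6.6 makes PPCV the principal inference for time to first severe flare, a multiplicity-controlled major secondary endpoint. It also makes PPCV the main set for the annualized severe flare rate. PP and AC are supplemental.

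**Severe-flare criteria (Appendix 5).** Criterion 4 is "Initiation of immunosuppressive therapy". Criterion 3 is "Increase in prednisone (or equivalent) to more than 0.5 mg/kg/day", limited "to patients who have a prednisone dose of" 0.5 mg/kg/day or less at baseline. Criterion 2 can be met through a prednisone increase or through hospitalization.

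**Prohibited changes (Table JAIA.6.2).** Starting an immunosuppressant is prohibited throughout treatment. So is raising corticosteroids above baseline, apart from the permitted burst, which is confined to the first 12 weeks. A re-increase during taper may not pass the baseline dose. Under Section 6.9 and Appendix 1, a blinded case-by-case review can clear a change.

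**Flare dates (Table JAIA.6.4).** SFI flares are taken as recorded, and time to first flare runs from first dose to the flare's own first date.

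**The concern.** One medication change can both close the exposure window and constitute the severe flare. Whether the flare counts then turns only on which of two separately recorded dates comes first. If the flare is dated later than the drug start that defines it, the event removes itself: it falls outside the window and the patient is censored at the moment treatment had to be escalated for lupus. That is informative censoring in the principal analysis of an alpha-controlled endpoint, and it carries over to the severe flare rate. Nothing in Section 6.4, Table JAIA.6.4 or Appendix 5 ties the two dates together or exempts such a flare. At stake are events, and hence power. If the loss differed between arms, the hazard ratio would move too.

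**Working it through.** **1. Where the event and the cut-off coincide.**
- Criterion 4: any immunosuppressant start is prohibited (Table JAIA.6.2), so the overlap lasts the whole treatment period.
- Criterion 3: an eligible patient starts at or below 0.5 mg/kg/day and rises above it. At constant weight that always exceeds the baseline dose, so the taper allowance cannot cover it. Only the burst can, and only up to Week 12. After that, every eligible criterion-3 flare is also a prohibited increase unless the review clears it. This covers (52 − 12)/52 = 40/52 = 77% of the treatment weeks, which is calendar time and not a share of flares.
- Criterion 2 overlaps in part (its steroid route). Criteria 1, 5 and 6 need no drug start.

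**2. The rule applied to invented dates**, with the prohibited drug started on day 140:
- flare dated day 139: event at day 139;
- flare dated day 140: event at day 140, if the cut-off day is inside the window;
- flare dated day 168: not counted, censored at day 140.

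**3. The plan's own figure.** The SAP gives no event count, hazard ratio or power for this endpoint. Its only power statement (Section 5.2) is for SRI-4: 250 per arm, 40% versus 57%, 2-sided 0.05, above 90%. It reproduces: pooled rate 0.485, null SE √(2×0.485×0.515/250) = 0.0447, alternative SE √((0.40×0.60 + 0.57×0.43)/250) = 0.0440, z = (0.17 − 1.96×0.0447)/0.0440 = 1.87, power 0.97.

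**4. Illustration for severe flares.** Only the 250 per arm and the 0.05 come from the SAP. Assumed: 52-week placebo severe-flare risk p0 and hazard ratio HR. The loss L is the share of severe flares that are medication-defined × the share of those dated after the drug start (Lp placebo, Lb baricitinib). Lost flares act as censoring:
- d = 250 × [(1 − Lp)·p0 + (1 − Lb)·(1 − (1 − p0)^HR)]
- HR_obs = HR × (1 − Lb)/(1 − Lp)
- power = Φ(√(d/4) × (−ln HR_obs) − 1.96)

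For p0 = 0.20, HR = 0.6 and no loss: 1 − 0.8^0.6 = 0.1253, d = 250 × 0.3253 = 81.3, and √(81.3/4) × 0.511 − 1.96 = 0.343, so power is 0.634.

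| p0 | Lp / Lb | events | HR_obs | power |
|---|---|---|---|---|
| 0.20 | 0 / 0 | 81.3 | 0.600 | 0.634 |
| 0.20 | 10% / 10% | 73.2 | 0.600 | 0.589 |
| 0.20 | 20% / 20% | 65.1 | 0.600 | 0.540 |
| 0.20 | 40% / 40% | 48.8 | 0.600 | 0.430 |
| 0.20 | 20% / 10% | 68.2 | 0.675 | 0.368 |
| 0.20 | 10% / 20% | 70.1 | 0.533 | 0.749 |
| 0.10 | 0 / 0 | 40.3 | 0.600 | 0.368 |
| 0.10 | 20% / 20% | 32.3 | 0.600 | 0.305 |

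Log-rank simulation (8,000 trials, p0 = 0.20, HR = 0.6) agrees for equal loss: 0.631, 0.585, 0.537 and 0.429 for 0, 10, 20 and 40%. For unequal loss it gives 0.365 (20% / 10%) and 0.725 (10% / 20%).

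**The case against.** The strongest reply is that the harm needs a dating habit the SAP does not show. Table JAIA.6.4 takes the first date of the flare, which reads as onset. The natural date for criteria 3 and 4 is the day of the drug change, and the worsening that prompts it comes earlier. On that reading nothing is lost. This stands, and it limits the size of the point.

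Same-day flares are also largely settled. Section 6.4 runs the window up to the cut-off date, and Table JAIA.6.5 excludes only observations after the intercurrent event. Sections 6.4.2.3 and 6.10.1 lean the same way for other endpoints. Stating it for this analysis is a clarification.

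Stopping at rescue is a deliberate strategy, and the AC analysis follows patients past it. Both are true. But disregarding flares that come after rescue differs from discarding the flare that the rescue itself constitutes. AC is supplemental and also drops the treatment-discontinuation cut-off, so it does not isolate this effect.

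A reader might infer more than the documents support:
- *That the principal analysis discards all medication-defined flares.* It does not; those dated on or before the drug start count.
- *That affected patients are treated as flare-free for 52 weeks.* They contribute risk time only up to the drug start.
- *That the hazard ratio is biased in a known direction.* Unequal loss would need dating to differ between arms of a double-blind trial, and no reason for that is apparent.
- *That the rule contradicts the PPCV question in Table JAIA.6.5.* That text is about achieving response and is weak evidence for a time-to-event endpoint.

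**Conclusion.** The point holds in a limited form and is minor. As written, the PPCV and PP rules drop a medication-defined severe flare dated after its own drug start and censor the patient at that start, so the censoring depends on the event. This follows from stated rules and is not merely missing detail. It applies to criterion 4 throughout, criterion 3 after Week 12 and part of criterion 2, except where the blinded review clears the change.

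Frequency and direction cannot be determined from the SAP, and the loss may be zero. The power and hazard-ratio figures rest on an assumed placebo risk, hazard ratio and loss share. They show sensitivity and do not estimate this trial's power. Under them, equal loss of 10 to 40% costs about 4 to 20 percentage points of power with the hazard ratio unchanged.

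**What to change.** In Section 6.4 and Appendix 5, for PPCV and PP:

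1. Count an eligible severe flare that meets an SFI criterion through the prohibited medication change itself as an event, dated at the earlier of the entered flare date and that medication start.
2. State this as an exception to the Table JAIA.6.4 rule that SFI flares are taken as recorded, because it overrides the entered date.
3. Apply the same rule in the annualized severe flare rate. Section 6.4 treats all collected flares as eligible there, so the Appendix 5 eligibility limits do not carry over.
4. State that the cut-off day lies inside the exposure window.

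PPCV stays principal. Optionally, add one supportive row to Table JAIA.6.6: time to first severe flare with the start of prohibited SLE medication, as classified by the existing blinded review, also counted as an event. That composite mixes rescue with flare, so it should only be supportive.

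**Cost.** A few lines of text, some programming, and a small rule linking each such flare to its medication record, including flares that meet several criteria at once. Medication dates are already collected. Appendix 5 already relies on a recorded cause, as in its example where a patient's "case report form indicates that they had a postbaseline flare due to glomerulonephritis".

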6.4.1 Adjustments for Covariates

Randomization is stratified according to disease activity (total SLEDAI-2K at screening <10; ≥ 10), corticosteroid dose at baseline (<10 mg/day; ≥ 10 mg/day prednisone or equivalent), and region (North America, Central/South America/Mexico, Europe, Asia and Rest of World). Therefore, these factors will be adjusted for as described in Section [6.4](#).

6.4.2 Handling of Dropouts or Missing Data

Depending on the estimand being addressed, different data cutoffs and imputation methods will be used to handle intercurrent events. [Table JAIA.6.5](#) and [Table JAIA.6.6](#) specify how data will be included and the associated imputation method for each analysis. Intercurrent events (ICEs) for Study JAIA include:

- Initiation/increase of prohibited medication
- Permanent study drug discontinuation (COVID or non-COVID reasons)
- Study discontinuation (COVID or non-COVID reasons)

- Intermittent missing visits or assessment (COVID or non-COVID reasons), and
- Temporary treatment interruptions due to COVID reasons.

6.4.2.1 Non-responder Imputation (NRI)

The non-responder imputation (NRI) method may be used when the estimand of interest uses the composite strategy (EMA 2020) for handling intercurrent events. In this strategy, patients will be considered non-responders for the NRI analysis if they do not meet the clinical response criteria or have missing clinical response data (based on each set of [Table JAIA.6.5](#)) at the analysis time point.

6.4.2.2 Mixed Model for Repeated Measures

For continuous variables, the primary analysis will be an MMRM analysis with a missing at random assumption for handling missing data. This likelihood-based analysis takes into account both missingness of data and the correlation of the repeated measurements.

The MMRM method may be justified when the estimand of interest uses the hypothetical strategy (EMA 2020) for handling intercurrent events. In this strategy, the scientific question of interest is to assess the effect of study treatment in a hypothetical trial where all patients have complete data and continue to take study treatment as directed without dropping out of the study.

6.4.2.3 Modified Last Observation Carried Forward (mLOCF)

Modified last observation carried forward will be used to impute missing data for analyses implementing ANCOVA or Wilcoxon rank-sum in the PP datapoint sets ([Table JAIA.6.5](#)), unless otherwise specified. For patients who receive prohibited medication, the last nonmissing observation at or before prohibited use will be carried forward to subsequent time points for evaluation. For all other patients discontinuing from the study or permanently discontinuing the study treatment for any reason, the last nonmissing postbaseline observation on or before discontinuation will be carried forward to subsequent time points for evaluation. If a patient has a missing record that cannot be imputed by other means for a postbaseline visit, the last postbaseline record prior to the missed visit will be used for this postbaseline visit.

6.4.2.4 Hybrid Imputation

Hybrid imputation will be conducted to adjust for the effect of missing data due to the COVID-19 pandemic on the clinical trial. Missing data due to the COVID-19 pandemic includes: 1) data collected during drug interruption due to COVID-19 while a patient is considered off-drug; or 2) data which were not collected due to the COVID-19 pandemic (that is, missing visit data, in part or in whole). For the selected binary and continuous endpoints (see [Table JAIA.6.6](#)), multiple imputation (MI) will be used for imputing data that is missing due to COVID-19 in the PPCV datapoint sets (see [Table JAIA.6.6](#), PPCV definition), whereas other missing data not due to COVID-19 will be imputed by NRI for the binary endpoints and by MMRM for the continuous endpoints.

This hybrid imputation procedure addresses the hybrid estimand assuming that the effects of treatments would be the same as the PP analysis, had patients not experienced any intercurrent

event related to COVID-19 (see Section 6.4.2). The algorithm for hybrid imputation on binary and continuous endpoints (see [Table JAIA.6.4](#)) is as follows:

1. Identify all missing data, either due to COVID-19 or otherwise. Note: data following ICEs described in Section 6.4.2, will be set to missing prior to Step 2. Any data after prohibited medication or treatment/study discontinuation due to non-COVID-19 reasons will be all considered as missing due to non-COVID-19 reasons.
2. Implement the MI via PROC MI FCS REG or PROC MI FCS LOGISTIC to impute all continuous or binary missing data, respectively with treatment arm and stratified variables as covariates and generate m imputed complete data sets.
3. For each of these m imputed complete data sets from Step 2, the imputed data for missing not due to COVID-19 (as in Step 1) will be set to missing and the imputation method specified in [Table JAIA.6.6](#) will be implemented. For all other data including imputed or observed will be used for the analysis or to derive the binary outcomes.
4. Single estimates will be combined using Rubin's rules (Rubin 1987) via PROC MIANALYZE.

The number of imputed data sets will be $m=25$ and a 6-digit initial seed value prespecified for each analysis as 123456.

For the composite binary endpoints such as SRI-4, BICLA and Lupus Low Disease Activity State (LLDAS) (see [Table JAIA.6.4](#)), the hybrid imputation algorithm will be applied on each binary component first. For each binary component, multiple imputation may be applied on the continuous variable and then dichotomized if needed.

For the corticosteroid sparing endpoint in the PPCV datapoint set, mLOCF will be conducted to handle the missing data for corticosteroid daily dose due to COVID-19 whereas missing data due to other reasons will be handled by NRI. The algorithm for hybrid imputation on Corticosteroid Sparing is as follows:

[figure not shown]
1. Identify all missing data, either due to COVID-19 or otherwise. Note: data following ICEs described in Section 6.4.2, will be set to missing prior to Step 2.
2. Implement the mLOCF to impute the missing data due to COVID-19.
3. The missing data not due to COVID-19 (as in Step 1) will be set to missing and the NRI method will be implemented. For all other data including imputed or observed will be used to derive the binary outcomes.

6.5 Multicenter Studies

For the analysis of the primary endpoint, assessment of the impact of regions will be specified within the integrated efficacy analysis plan.

6.6 Multiple Comparisons/Multiplicity

A prespecified graphical multiple testing approach (Bretz et al. 2009, 2011) will be implemented to control the overall Type I error rate at 2-sided alpha of 0.05, for all primary and major secondary endpoints. The graphical approach is a closed testing procedure; hence, it strongly controls the familywise error rate across all endpoints (Alosh et al. 2014). Details of the graphical testing scheme (including testing order, interrelationships, Type I error allocation, and the associated propagation) are included below (see [Figure JAIA.6.1](#)). Each hypothesis is represented as a node in a graph. Directed arrows between the nodes with associated weights represents how alpha is passed from its initial allocation to other nodes. The testing scheme was finalized before the first unblinding of the study team to efficacy data. Unless otherwise specified, there will be no adjustment for multiple comparisons for any other analyses.

Abbreviations: FACIT-F = Functional Assessment of Chronic Illness Therapy-Fatigue; LLDAS = Lupus Low Disease Activity State; SRI-4 = Systemic Lupus Erythematosus Responder Index-4; TTE = time to event; W = week.

Note: All tests are compared to placebo. All hypothesis tests contained within a box must be rejected before alpha is passed on.

Figure JAIA.6.1. **Illustration of graphical multiple testing procedure with initial α allocation and weights.**

